13.4.3. Record Retention

All study records must be retained in strict accordance with the Clinical Trial Agreement executed between Ultragenyx and the Institution and/or Investigator. For study monitoring, audit, or inspection, the IRB/IEC and Sponsor or its designees have the right to access all CRFs, source documents, and other study documentation. The Investigator or study site will retain such

documents from the start of the study to at least 25 years after the close of the study, guarantee access to these documents, and cooperate with and support such audits and inspections.

13.5. Financing and Insurance

Financing and insurance for this clinical study will be addressed in the Clinical Trial Agreement between Ultragenyx and the Institution and/or Investigator.

13.6. Publication Policy

Any publication or presentation by the Investigator and/or the Institution associated with the study will be in strict accordance with the Clinical Trial Agreement executed between Ultragenyx and the Institution and/or Investigator.

15. APPENDICES

APPENDIX 1. PROMIS-29

APPENDIX 2. PROMIS SOCIAL ISOLATION – SHORT FORM 4A

APPENDIX 3. PITTSBURGH SLEEP QUALITY INDEX (PSQI)

APPENDIX 4. PATIENT GLOBAL IMPRESSION OF SEVERITY (PGI-S)

APPENDIX 5. PATIENT GLOBAL IMPRESSION OF CHANGE (PGI-C)

1. INTRODUCTION AND OBJECTIVES OF ANALYSIS

1.1. Introduction

Study 401GSDIA02 is a long-term follow-up study to evaluate the safety and efficacy of adeno-associated virus serotype 8 (AAV8)-mediated gene transfer of glucose-6-phosphatase (G6Pase) in adults with glycogen storage disease type Ia (GSDIa). Only subjects who received DTX401 in Study 401GSDIA01 are eligible to participate in Study 401GSDIA02. Study 401GSDIA01 was a Phase 1/2, open-label safety and dose-finding study of AAV8-mediated gene transfer of G6Pase in adults with GSDIa, during which subjects received a single intravenous (IV) dose of DTX401. No investigational product will be administered during Study 401GSDIA02.

1.2. Objectives of Analysis

The purpose of this Statistical Analysis Plan (SAP) is to provide details of the statistical analyses that have been outlined within the 401GSDIA02 Protocol Amendment 4 dated 3 April 2023.

2. STUDY OBJECTIVE(S)

2.1. Primary Objective(s) and Endpoint(s)

The primary objective of the study is as follows:

- To determine the long-term safety of DTX401 following a single IV dose in adults with GSDIa

The primary endpoint of this study is as follows:

- The incidence of AEs and SAEs for each cohort and overall assessed by severity and relationship to IP

2.2. Secondary Objective(s) and Endpoint(s)

The secondary objective of the study is as follows:

- To evaluate the long-term effect of DTX401 on symptom-free euglycemia in a setting of a controlled fasting challenge

The secondary endpoint of this study is as follows:

- The change from Day 0 (Study 401GSDIA01) in time to first hypoglycemic event during a controlled fasting challenge over time by cohort and overall, following IV administration of DTX401

2.3. Tertiary Objectives and Endpoints (s)

The tertiary objectives of this study are as follows:

- To evaluate the long-term effect of DTX401 on lipid profiles (total cholesterol, low-density lipoprotein, and triglycerides)
- To evaluate the long-term effect of DTX401 on uric acid
- To evaluate the long-term effect of DTX401 on proteinuria
- To evaluate the long-term effect of DTX401 on liver size and fat content
- To evaluate the long-term effect of DTX401 on hepatic adenoma progression
- To assess the long-term impact of DTX401 on cornstarch requirements
- To assess the long-term impact of DTX401 on glucose homeostasis
- To assess the long-term impact of DTX401 on the subject's health-related quality of life (HRQoL) and sleep quality
- To describe the long-term immune response to AAV8 capsid proteins after IV administration of DTX401
- To describe the long-term immune response to G6Pase after IV administration of DTX401
- To evaluate the long-term effect of DTX401 on lactate levels

- To evaluate the long-term effects of DTX401 on the endocrine and metabolic responses to fasting

The tertiary endpoints of this study are as follows:

- Total cholesterol, low-density lipoprotein, and triglycerides, by time point, cohort, and overall
- Uric acid, by time point, cohort, and overall
- 24-hour urine protein, by time point, cohort, and overall
- The change from baseline in liver size and fat fraction (by MRI) over time following IV administration of DTX401, by cohort, and overall
- The average daily use of cornstarch (or equivalent) over time, by cohort, and overall
- Assessment of serum glucose levels over time, summarized by cohort
- Subject responses to HRQoL and sleep quality assessments over time following IV administration of DTX401, by cohort and overall
- Year 2 – Exit Interviews
- The development of neutralizing antibodies to AAV8 (as determined by a cell-based assay) over time, by cohort, and overall
- The development of anti-AAV8 binding antibodies (as determined by ELISA) over time, by cohort, and overall
- The development of anti-G6Pase antibodies over time, by cohort, and overall
- Assessment of lactate levels over time, summarized by cohort and overall

2.4. Estimands

Not applicable.

3. STUDY DESIGN

In Study 401GSDIA01, subjects were followed for 1 year after dosing with DTX401. In Study 401GSDIA02, subjects will be followed for at least 3 additional years (and up to 5 additional years) for a total of 4-6 years of follow-up after administration of DTX401.

The first visit for Study 401GSDIA02 (Visit 1) may coincide with the Week 52/EOS/EW visit for Study 401GSDIA01. Subjects will visit the study site approximately every 13 weeks during the first year of Study 401GSDIA02 and then approximately every 26 weeks through the end of the study at Week 312 (Year 6) for safety and efficacy evaluations.

A long-term disease monitoring program (DMP) DTX401-CL401 is planned. Once the DMP is available to enroll, and after subjects reach the Week 208 visit (Year 4) in Study 401GSDIA02, subjects will transition to the DMP with Sponsor approval.

3.1. Study Population

Subjects dosed with DTX401 in Study 401GSDIA01 and who have met eligibility criteria for Study 401GSDIA02 study will be enrolled in Study 401GSDIA02.

3.2. Dosage and Administration

No investigational product will be administered during Study 401GSDIA02. All subjects enrolled in Study 401GSDIA02 will have received a single IV dose of DTX401 during their participation in Study 401GSDIA01.

3.3. Blinding and Randomization Methods

Not applicable.

3.4. Potential Covariate(s)

Not applicable.

3.5. Subgroups

Not applicable.

3.6. Sample Size Considerations

The study is expected to enroll up to 12 subjects. The sample size is not based on a power calculation.

3.7. Statistical Hypothesis

No formal statistical hypothesis testing will be performed.

3.8. Multiple Comparisons/Multiplicity

Not applicable.

3.9. Interim Analysis

Administrative analyses may be performed during the study to support registrational activities or respond to regulatory inquiries.

3.10. Data Monitoring Committee

Not Applicable.

4. DEFINITIONS

4.1. Baseline

Baseline is defined as the last non-missing assessment taken prior to the dose of DTX401 in Study 401GSDIA01, unless specified otherwise.

4.2. Study Day

If the visit date is on or after the date of the dose of DTX401:

$$\text{Study day} = (\text{visit date} - \text{date of the dose of DTX401} + 1)$$

If the visit date is prior the date of the dose of DTX401:

$$\text{Study day} = \text{visit date} - \text{date of the dose of DTX401}.$$

4.3. Patient-Reported Outcomes Measurement Information System (PROMIS)

The PROMIS was developed by the National Institutes of Health and uses domain-specific measures to assess patient well-being (Broderick et al., 2013), (NIH, 2015). It uses a T-score metric in which 50 is the mean of a relevant reference population and 10 is the standard deviation (SD) of that population. High scores indicate more of the concept being measured. The domain-specific approach is based on the idea that health attributes, such as pain and physical function are not unique to a specific disease. The PROMIS contains a bank of questions from which relevant items can be extracted and used to create a custom form.

The PROMIS-29 profile (v2.1) (Appendix 3) is a profile measure designed for adults that includes a collection of seven 4-item short forms assessing domain scores for anxiety, depression, fatigue, pain interference, physical function, sleep disturbance, and ability to participate in social roles and activities as well as a single pain intensity item. The single pain intensity item is not scored but reported as its raw score (e.g., 0 to 10).

Each domain has one or more items, and each item has five response options ranging in value from 1 to 5. The score interpretation is included in Table 1.

Table 1: Numerical Scoring of Adult Domains

	Worst Score	Best Score
Physical Function/Ability to Participate in Social Roles and Activities	1	5
Fatigue/Sleep Disturbance/Pain Interference /Cognitive Function/Anxiety/Depression	5	1

[figure not shown]
The raw score for a domain can be derived as follows:

$$\frac{\text{Raw sum} \times \text{number of items on the domain}}{\text{Number of items that were actually answered on the domain}}$$

The PROMIS Social Isolation ([Appendix 4](#)) is a 4-item short form assessing perceptions of being avoided, excluded, detached, disconnected from, or unknown by, others.

4.4. Pittsburgh Sleep Quality Index

CCI

4.5. Patient Global Impression of Severity (PGI-S) And Patient Global Impression of Change (PGI-C)

The 5-point PGI-S instrument will be administered to ascertain patient perception of disease severity ([Appendix 6](#)). The PGI-C is a self-completed measure to assess the patient's view of improvement from baseline and is rated on a 7-point categorical scale ranging from 'much improved' to 'much worse' ([Appendix 7](#))

5. ANALYSIS SETS

5.1. Full Analysis Set (FAS)

The full analysis set will consist of all subjects enrolled in Study 401GSDIA02 and have received a dose of DTX401 in Study 401GSDIA01. Unless specified otherwise, the full analysis set will be used for all the analyses.

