8.2. Exclusion Criteria

Individuals who meet any of the following exclusion criteria will not be eligible to participate in the study:

1. Planned or current participation in any other interventional clinical study that may confound the safety or efficacy evaluation of DTX401 during this study
2. Presence or history of any condition that, in the view of the Investigator, poses a risk to subject safety or places the subject at high risk of poor compliance or not completing the study or that would significantly affect the interpretation of study results

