6. STATISTICAL ANALYSIS

6.1. General Principles

All analyses in the study will be descriptive; no formal hypotheses will be tested. An integrated analysis using data from both Study 401GSDIA01 and Study 401GSDIA02 will be performed to summarize and assess the long-term safety and efficacy of DTX401; there will not be a standalone analysis of data from only Study 401GSDIA02.

Continuous variables will be summarized by number of subjects, mean, SD, standard error (SE), median, Q1, Q3, minimum, and maximum values. Categorical variables will be summarized by number and percentage of subjects. All summary tables will be presented by scheduled study visit and no analysis windows will be used, unless specified otherwise. Study visits from both studies 401GSDIA01 and 401GSDIA02 will be included in summary tables.

All summary tables will be presented by dose cohort of DTX401 (see below), Cohorts 2, 3, 4 combined (i.e., cohorts for dose 2 combined), and overall, unless specified otherwise.

The dosing cohorts are:

- Cohort 1: Dose 1 (2.0×10^{12} GC/kg) with a reactive steroid regimen (prednisone starting dose of 40 mg/day)
- Cohort 2: Dose 2 (6.0×10^{12} GC/kg) with a reactive steroid regimen (prednisone starting dose of 40 mg/day)
- Cohort 3: Dose 2 (6.0×10^{12} GC/kg) with an optimized reactive steroid regimen (prednisone starting dose of 60 mg/day)
- Cohort 4: Dose 2 (6.0×10^{12} GC/kg) with a prophylactic steroid regimen

SAS[®] software version 9.4 or higher will be used to perform statistical analyses unless otherwise specified.

Handling of missing or incomplete data is described in [Appendix 1](#).

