6.8. Efficacy Analysis

The efficacy analyses will be based on the Full Analysis Set.

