6.9. Safety Analysis

The safety analysis will be performed using the FAS. The safety parameters will include AEs, SAEs, vital sign measurements, physical examination findings, electrocardiogram (ECG) results, subject reported symptomatic hypoglycemic events, clinical laboratory assessments (clinical chemistry [including liver function tests], hematology, coagulation panel, and urinalysis), vector shedding, vector genome determination, measurement of neutralizing antibody titer to AAV8, measurement of AAV8 binding antibody immunoglobulin G (IgG), assessment of any cell-mediated immune responses to AAV8 and G6Pase, and measurement of anti-G6Pase antibodies.

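### The only analysis set requires enrolment in the follow-up study, yet it is applied to summaries that start at dosing; any dosed subject who did not roll over drops out of the year-1 and cumulative denominators

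*SAP*

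**What the plan says.** SAP 5.1 defines a single analysis set, "all subjects enrolled in Study 401GSDIA02 and have received a dose of DTX401 in Study 401GSDIA01", and adds: "Unless specified otherwise, the full analysis set will be used for all the analyses". SAP 6.8 repeats this for efficacy ("The efficacy analyses will be based on the Full Analysis Set") and SAP 6.9 for safety ("The safety analysis will be performed using the FAS"). No set of all dosed subjects is defined.

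The data placed on that set cover both studies. SAP 6.1 states: "An integrated analysis using data from both Study 401GSDIA01 and Study 401GSDIA02 will be performed to summarize and assess the long-term safety and efficacy". It continues: "Study visits from both studies 401GSDIA01 and 401GSDIA02 will be included in summary tables". SAP 6.9.1 combines adverse events from the two studies, counts them as treatment-emergent from dosing, and tabulates them by year since administration, starting with a window of less than 1 year. SAP 6.8.1 pools CFC duration from both studies, and SAP 6.9.3 does the same for laboratory values.

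Protocol 12.3.1 likewise restricts the analyses to subjects enrolled in Study 401GSDIA02. Protocol 12.2.1 asks for enrolled subjects who were dosed but does not name the study; the SAP settles it on the follow-up study. SAP 7 declares no change from the protocol.

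**The concern.** Dosing is time zero for the integrated tables, but membership of the set is decided later, by consent and eligibility for a second study. A dosed subject who did not enter the follow-up is removed from the later visits, where there are no data anyway, and also from the year-1 columns and the cumulative adverse event tables, where Study 401GSDIA01 data exist.

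The protocol allows this to happen. Protocol 12.1.4 makes enrolment depend on meeting the eligibility criteria, Protocol 8.1 requires new consent, and the second exclusion in Protocol 8.2 begins: "Presence or history of any condition that, in the view of the Investigator, poses a risk to subject safety". SAP 6.2 provides a listing for subjects who fail the criteria.

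Year 1 matters for safety here. SAP 6.9.1.1 and 6.9.1.2 do not expect infusion-related reactions, or corticosteroid use for vector-induced hepatic events, in the follow-up because subjects enter at 52 weeks. On the SAP's own reasoning, those risks belong mainly to the period in which a missing subject's data would be left out. With cohorts of 3, one subject is a third of a cohort.

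**Working it through.** **Inputs**
- Subjects in Study 401GSDIA01: 4 cohorts × 3 = 12, which reproduces the stated total (Protocol 5.4). Three cohorts received Dose 2, so 3 × 3 = 9. I assume that all 12 were dosed.
- Number who did not enrol in Study 401GSDIA02: not given. I call it *k* and take 0 to 3 as an assumed range.
- No alpha, power or effect size enters. SAP 3.6 and 3.7 make the study descriptive, with no power calculation.

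**Denominators**

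Under the SAP's set: overall 12 − *k*; Dose 2 combined 9 − *k* if all losses are there; a single cohort as low as 3 − *k*. With an all-dosed set they stay at 12, 9 and 3 whatever *k* is.

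**Case 1: the event occurred only in the missing subject (*k* = 1)**
- All dosed: 1/12 = 8.3% (exact 95% interval 0.2% to 38.5%).
- SAP set: 0/11 = 0%. The exact two-sided 95% upper bound is 1 − 0.025^(1/11) = 28.5%.
- Within that subject's cohort: 1/3 becomes 0/2.

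**Case 2: 3 of the 12 dosed had the event (25.0%)**

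The displayed figure lies between (3 − *k*)/(12 − *k*), if all the missing subjects had the event, and 3/(12 − *k*), if none did.

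| *k* | Overall N | Lowest displayed | Highest displayed |
|---|---|---|---|
| 0 | 12 | 3/12 = 25.0% | 3/12 = 25.0% |
| 1 | 11 | 2/11 = 18.2% | 3/11 = 27.3% |
| 2 | 10 | 1/10 = 10.0% | 3/10 = 30.0% |
| 3 | 9 | 0/9 = 0% | 3/9 = 33.3% |

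The direction depends on who is missing. At *k* = 0 the two sets are identical. At *k* = 3 a whole cohort could be empty.

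The same conditioning applies to mean CFC duration and laboratory changes in year 1. The documents contain no individual values from which to size it.

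**The case against.** **Full rollover is plausible.** Protocol 7.1.2 plans for about 12 subjects, which is the whole of the parent study. Protocol 7.1.3.2 says, in the past tense, that everyone dosed was eligible. That protocol version (April 2023) postdates completion of Study 401GSDIA01 in November 2022 (Protocol 5.2.3). This stands as a reason to treat the problem as conditional. It does not settle it: being eligible is not the same as enrolling, and Protocol 12.1.4 and SAP 3.6 still give an expected number rather than an actual count.

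**Early withdrawal does not bar entry.** Protocol 7.1.3.4 lets a subject who left Study 401GSDIA01 before Week 52 enrol later on an adjusted schedule. A reader might infer that the year-1 columns describe only subjects who were well and still participating at Week 52. The documents do not support that.

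**Year-1 results have another home.** SAP 6.5 to 6.7 refer to a separate clinical study report for Study 401GSDIA01. Those sections describe its demographic, medical history and medication summaries, not its adverse event or CFC tables, but it is the natural place for all-dosed year-1 results. The gap shown here is therefore in the integrated tables, not in all reporting.

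**The analysis is descriptive, and following the same people from baseline is a defensible display.** Both are true, and individual listings help. The SAP 6.2 listing also gives the criteria failed by an ineligible subject. It does not cover a dosed subject who never consented, and no listing restores a denominator.

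**Conclusion.** The mismatch between the analysis set and the period summarised is real and follows directly from SAP 5.1, 6.1, 6.8 and 6.9. Whether it has any effect depends on the rollover count, which neither document states. With full rollover there is none. With one subject missing, a 25.0% incidence is displayed as 18.2% or 27.3%, and an event confined to that subject disappears from the integrated tables (8.3% to 0%, upper bound 28.5%).

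A reader might infer that the plan biases the results in favour of DTX401. The documents do not support this: nothing shows that anyone failed to roll over, and the error is favourable only if non-enrolment was related to a poor outcome. The sizes above rest on all 12 parent-study subjects having been dosed and on assumed values of *k*.

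**What to change.** 1. Define in SAP 5 an all-dosed set: every subject dosed in Study 401GSDIA01, each contributing data until last contact. Use it for the integrated adverse event, laboratory and CFC summaries.
2. Keep the current Full Analysis Set for tables restricted to Study 401GSDIA02, such as the separate adverse event summary in SAP 6.9.1.
3. In SAP 6.2, report by cohort the numbers dosed, rolled over and not rolled over, with reasons that include refusal of consent as well as failed criteria.
4. Align Protocol 12.2.1 and 12.3.1 with this, or record the difference in SAP 7.

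The cost is wording and one disposition table. The Study 401GSDIA01 data are already to be pooled, so nothing new is collected. If all 12 enrolled, the two sets coincide, no number changes, and a sentence in the SAP saying so closes the point.

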6. STATISTICAL ANALYSIS

6.1. General Principles

All analyses in the study will be descriptive; no formal hypotheses will be tested. An integrated analysis using data from both Study 401GSDIA01 and Study 401GSDIA02 will be performed to summarize and assess the long-term safety and efficacy of DTX401; there will not be a standalone analysis of data from only Study 401GSDIA02.

Continuous variables will be summarized by number of subjects, mean, SD, standard error (SE), median, Q1, Q3, minimum, and maximum values. Categorical variables will be summarized by number and percentage of subjects. All summary tables will be presented by scheduled study visit and no analysis windows will be used, unless specified otherwise. Study visits from both studies 401GSDIA01 and 401GSDIA02 will be included in summary tables.

All summary tables will be presented by dose cohort of DTX401 (see below), Cohorts 2, 3, 4 combined (i.e., cohorts for dose 2 combined), and overall, unless specified otherwise.

The dosing cohorts are:

- Cohort 1: Dose 1 (2.0×10^{12} GC/kg) with a reactive steroid regimen (prednisone starting dose of 40 mg/day)
- Cohort 2: Dose 2 (6.0×10^{12} GC/kg) with a reactive steroid regimen (prednisone starting dose of 40 mg/day)
- Cohort 3: Dose 2 (6.0×10^{12} GC/kg) with an optimized reactive steroid regimen (prednisone starting dose of 60 mg/day)
- Cohort 4: Dose 2 (6.0×10^{12} GC/kg) with a prophylactic steroid regimen

SAS[®] software version 9.4 or higher will be used to perform statistical analyses unless otherwise specified.

Handling of missing or incomplete data is described in [Appendix 1](#).

6.2. Subject Accountability

The number and percentage of subjects who complete Study 401GSDIA02 and of subjects who prematurely discontinue Study 401GSDIA02 will be summarized. The reasons for premature discontinuation from the study will be summarized as recorded in the electronic case report forms (eCRFs). The study duration will be summarized. The study duration is defined as date of Study 401GSDIA02 completion/discontinuation – DTX401 dose date +1. Number of subjects completing 1, 2, 3, 4, 5, and 6 years of study will be provided. A subject disposition listing, including study duration, will be provided.

For subjects who fail to meet eligibility criteria for Study 401GSDIA02, the inclusion/exclusion criteria the subjects fail will be listed.

6.3. Protocol Deviations

Major protocol deviations in Study 401GSDIA02 will be summarized for each type. Both major and minor protocol deviations will be listed.

6.4. Investigational Product Administration

Not applicable because no investigational product (IP) will be administered during Study 401GSDIA02.

6.5. Demographic and Baseline Characteristics

Demographic and baseline data captured in Study 401GSDIA01 is summarized and listed as part of the clinical study report for that study; demographic information captured in Study 401GSDIA02 at the study entry will not be summarized or listed separately.

